Clearance of baseline pathogen nucleic acid from a specimen taken at the TOC Visit, without the participant receiving other systemic antimicrobials before this visit	Nucleic acid clearance	NAAT success
Persistence of baseline pathogen nucleic acid from a specimen taken at the TOC Visit, without the participant receiving other systemic antimicrobials before this visit	Nucleic acid persistence	NAAT failure ^a
1) A determination of the nucleic acid outcome from a specimen taken at the TOC Visit cannot be made (e.g., no sample taken, sample lost, visit did not occur) 2) The participant received other systemic antimicrobials before the TOC Visit	Unable to determine	NAAT failure ^a

NAAT=nucleic acid amplification test; NG=*Neisseria gonorrhoeae*; TOC = Test-of-Cure.

Note: Specimen refers to either a urogenital, pharyngeal, or rectal specimen obtained for NAAT. The NAAT outcomes are determined on a per-pathogen basis.

a. Participants who are a “NAAT failure” at the TOC Visit assessment yet are not switched to other systemic antimicrobials are evaluable at subsequent time points.

Table 7 Determining NAAT Outcome and Response at the Follow-Up Visit (Pharyngeal NG and Mgen Only)

Defining Criteria	NAAT Outcome	NAAT Response
Clearance of baseline pathogen nucleic acid from a specimen taken at the Follow-up Visit, without the participant receiving other systemic antimicrobials before this visit	Nucleic acid clearance	NAAT success
Persistence of baseline pathogen nucleic acid from a specimen taken at the Follow-up Visit, without the participant receiving other systemic antimicrobials before this visit	Nucleic acid persistence	NAAT failure
A determination of the nucleic acid outcome from a specimen taken at the Follow-up Visit cannot be made (e.g., no sample taken, sample lost, visit did not occur) Note: Any participants who received other systemic antimicrobials before the Follow-up Visit will not be evaluated for NAAT outcome or response at the Follow-up Visit	Unable to determine	NAAT failure

Mgen=*Mycoplasma genitalium*; NAAT=nucleic acid amplification test; NG=*Neisseria gonorrhoeae*.

Note: Specimen refers to either a urogenital or pharyngeal specimen obtained for NAAT. The NAAT outcomes are determined on a per-pathogen basis and will only be conducted if both the Baseline (NG and Mgen) and TOC (NG only) NAAT assay showed the presence of nucleic acid for the respective pathogen and specimen.

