7.3.1.5. NAAT outcome and response

- Variables: NAAT outcome and response will be determined by pathogen (NG or Mgen), body site (as applicable), for the TOC and FU visits as follows:
 - Those participants who have NG detected from their baseline NAAT specimen (urogenital, pharyngeal, rectal) will be evaluated for NAAT outcome and response at TOC visit for urogenital, pharyngeal, rectal respectively. For baseline pharyngeal NG confirmed participants, NAAT specimen will be evaluated at follow up visit as well if both the baseline and TOC pharyngeal NAATs were positive. Participants who have Mgen nucleic acid detected from their baseline NAAT specimen will be evaluated for Mgen NAAT outcome and response at follow up visit. The NAAT outcome and

response to study treatment will be determined by prespecified programmed algorithm for each participant (see Table 3).

- The NAAT outcome will be determined by comparing the baseline NAAT result with the respective NAAT result at each subsequent visit. The corresponding NAAT response (success or failure) by participant will then be assigned. The criteria for determining NAAT outcome and response are shown in Table 3 and Table 4.
- Participants who are a NAAT failure at the TOC visit but have not switched to other systemic antimicrobials with activity against NG are evaluable at FU visit (applicable to pharyngeal NG only).
- Participants who received other systemic antimicrobials on or after the TOC visit will be categorized as Unable to determine for NAAT outcome or response at the FU visit.

Table 3 NAAT Outcome and Response at the TOC Visit (NG Only)

Defining Criteria	NAAT Outcome	NAAT Response
Clearance of baseline pathogen nucleic acid from a specimen taken at the TOC visit, without the participant receiving other systemic antimicrobials before this visit	Nucleic acid clearance	NAAT success
Persistence of baseline pathogen nucleic acid from a specimen taken at the TOC visit, without the participant receiving other systemic antimicrobials before this visit	Nucleic acid persistence	NAAT failure ^a
1) A determination of the nucleic acid outcome from a specimen taken at the TOC visit cannot be made (e.g., no sample taken, sample lost, visit did not occur) 2) The participant received other systemic antimicrobials before the TOC visit	Unable to determine	NAAT failure ^a

NAAT=Nucleic Acid Amplification Test; NG=*Neisseria gonorrhoeae*; TOC = Test-of-Cure.

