Note: Specimen refers to either a urogenital, pharyngeal, or rectal specimen obtained for NAAT. The NAAT outcomes are determined on a per-pathogen and per-specimen source basis.

- a. Participants who are a “NAAT failure” at the TOC visit assessment yet are not switched to other systemic antimicrobials are evaluable at subsequent time points.

Table 4 NAAT Outcome and Response at the FU Visit (Pharyngeal NG and Urogenital Mgen Only)

Defining Criteria	Microbiological Outcome	Microbiological Response
Clearance of baseline pathogen nucleic acid from a specimen taken at the FU visit, without the participant receiving other systemic antimicrobials before this visit	Nucleic acid clearance	NAAT success
Persistence of baseline pathogen nucleic acid from a specimen taken at the FU visit, without the participant receiving other systemic antimicrobials before this visit	Nucleic acid persistence	NAAT failure
A determination of the nucleic acid outcome from a specimen taken at the Follow-up Visit cannot be made (e.g., no sample taken, sample lost, visit did not occur) Note: Any participants who received other systemic antimicrobials before the Follow-up Visit will not be evaluated for NAAT outcome or response at the Follow-up Visit	Unable to determine	NAAT failure

Mgen=*Mycoplasma genitalium*; NAAT=Nucleic Acid Amplification Test; NG=*Neisseria gonorrhoeae*.

Note: Specimen refers to either a urogenital or pharyngeal specimen obtained for NAAT. The NAAT outcomes are determined on a per-pathogen and per-specimen source basis and will only be conducted if either the Baseline (NG or Mgen) and TOC (NG only) NAAT assay showed the presence of nucleic acid for the respective pathogen and specimen.

Note: Participants who are a “NAAT failure” at the TOC visit assessment yet are not switched to other systemic antimicrobials are evaluable at subsequent time points.

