- k. At Follow-up, a pharyngeal specimen will be collected for detection of NG and CT by NAAT from participants whose NAAT assay had the presence of nucleic acid for NG at both Baseline and TOC. NAAT assay results will be available to the study sites by the Follow-up Visit.

Table 7 BTZ116577 NAAT Overview by Body Site and Organism

Body site	Organism	Baseline Visit			TOC Visit		F/U Visit	
		Local Lab	Central Lab		Central Lab		Central Lab	
			Real Time	Batch	Real Time	Batch	Real Time	Batch
Urogenital	NG/CT	X	X		X			
	MGen			X				X ^b
Pharyngeal ^a	NG/CT		X		X		X ^c	
Rectal ^a	NG/CT		X		X			

NG = *N. gonorrhoeae*; CT = *C. trachomatis*; MGen = *M. genitalium*; RT = real time (processed upon arrival); F/U=Follow-up.

a. Optional (upon patient consent)

b. Only if positive NAAT at baseline visit. MG NAATs will be run weekly by the central lab, so that baseline and results are back to the site in time for F/U.

c. Only if positive NG NAAT at baseline and TOC visit. Sites will have baseline and TOC pharyngeal NAAT results back by F/U

Note: Only central laboratory NAAT results will be used in the exploratory analysis, local lab NAAT is conducted to guide therapy at the TOC visit (*Chlamydia trachomatis*)

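### The note under SAP Table 4 garbles the both-positive NAAT condition for Follow-up; read as either/or, it would score participants who cleared pharyngeal NG at TOC as failures in one exploratory analysis

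*SAP*

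**What the plan says.** Protocol Section 9.1.2, in the note under its Table 7, says Follow-up NAAT outcomes "will only be conducted if both the Baseline (NG and Mgen) and TOC (NG only) NAAT assay showed the presence of nucleic acid". The SAP's copy of that note, under its Table 4 in Section 7.3.1.5, says they "will only be conducted if either the Baseline (NG or Mgen) and TOC (NG only) NAAT assay showed the presence of nucleic acid". SAP Section 2.1 states that the planned analyses in protocol amendment 3 were not changed.

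Elsewhere the rule for pharyngeal NG is consistent:

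- SAP Section 7.3.1.5, body text: the "NAAT specimen will be evaluated at follow up visit as well if both the baseline and TOC pharyngeal NAATs were positive".
- SAP Section 12.1.1, Table 6 footnote k: a Follow-up pharyngeal specimen is taken "from participants whose NAAT assay had the presence of nucleic acid for NG at both Baseline and TOC". Protocol Table 2 and the text of protocol Section 9.1.2 give the same sampling rule.
- SAP Section 12.1.1, Table 7 footnote c: "Only if positive NG NAAT at baseline and TOC visit".
- SAP Section 4, ME NAAT FU Pharyngeal Population: positive at Baseline and TOC, with a Follow-up result available.

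For Mgen, the SAP text requires a positive Baseline NAAT only.

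The third row of SAP Table 4 covers the case where "A determination of the nucleic acid outcome from a specimen taken at the Follow-up Visit cannot be made (e.g., no sample taken", among other reasons. It assigns an outcome of unable to determine and a response of NAAT failure. Footnote a of SAP Table 3, which is also in protocol Table 6, says that TOC NAAT failures "yet are not switched to other systemic antimicrobials are evaluable at subsequent time points".

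**The concern.** Pharyngeal Follow-up NAAT is analysed in two populations: ME NAAT FU Pharyngeal and Micro-ITT Pharyngeal (table of planned analyses in SAP Section 7.3.1.5; displays 2.339 and 2.338). The first carries its own both-positive condition. The second is defined in SAP Section 4 by a baseline pharyngeal culture and has no NAAT condition, and the entry for display 2.338 adds none. The wording of Section 7.3.1.5 therefore decides who is counted in that row, and the note under Table 4 does not match the body text.

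The choice matters because of the sampling design. A participant who was positive at Baseline and negative at TOC has no Follow-up pharyngeal swab. If that participant is admitted to the Follow-up denominator, the third row of Table 4 makes him or her a failure. Early clearance would count against an arm in a row for which an unadjusted between-arm difference and CI are planned.

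**Working it through.** The documents give no figure for this point, so there is none to reproduce. The check has two parts.

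**1. Who enters the Micro-ITT Pharyngeal Follow-up denominator**

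| Baseline NAAT | TOC NAAT | Follow-up swab by schedule | Both-positive rule | Note read as either/or |
|---|---|---|---|---|
| positive | positive | yes | counted, scored on result | counted, scored on result |
| positive | negative | no | not counted | counted, scored as failure |
| positive | no result | no | not counted | counted, scored as failure |

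The last line can also arise without the word *either*. Table 3 labels a missing TOC result a NAAT failure, and footnote a then makes that participant evaluable at Follow-up. This conflicts with the both-positive sentence in the same section. Footnote a does not reach the second line, because a participant who cleared at TOC is a NAAT success in Table 3.

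**2. Size under the either/or reading**

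Inputs, all assumed because the documents give no rates: N Baseline-positive participants per arm; c, the share cleared at TOC; r, later clearance among those still positive, taken as equal in both arms. No other data are missing and no other antimicrobials are used.

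- Both-positive rule: denominator N(1-c), success rate r.
- Either/or reading: denominator N, success rate (1-c)r.
- Cumulative clearance, for reference: c + (1-c)r.

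One arm, N = 40, c = 0.7, r = 0.5: the both-positive rule gives a denominator of 40 × 0.3 = 12 and 50% success. The either/or reading gives a denominator of 40 and 0.3 × 0.5 = 15% success, with 40 × 0.7 = 28 failures created by the design.

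Two arms:

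| c (arm A v arm B) | r | Both-positive | Either/or | Either/or difference | Cumulative clearance |
|---|---|---|---|---|---|
| 90% v 70% | 50% | 50% v 50% | 5% v 15% | -10 points | 95% v 85% |
| 95% v 80% | 50% | 50% v 50% | 2.5% v 10% | -7.5 points | 97.5% v 90% |
| 80% v 60% | 30% | 30% v 30% | 6% v 12% | -6 points | 86% v 72% |

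First line worked: (1 - 0.9) × 0.5 = 5%; (1 - 0.7) × 0.5 = 15%; difference -10 points. With equal r above zero, the difference is -(cA - cB)r, so it always runs against the arm with better TOC clearance.

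**The case against.** The strongest reply is that the note does not set an either/or rule.

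- It has no *or* between Baseline and TOC. In the same phrase the SAP changed the protocol's pairing of the pathogens from *and* to *or*, so *either* may have been meant for NG or Mgen.
- It is an *only if* condition, so it is necessary and not sufficient. A programmer who applies the both-positive sentence in the body text satisfies the note on any reading.
- The body text of Section 7.3.1.5 also says which TOC participants stay evaluable at Follow-up for pharyngeal NG: those who are NAAT failures at TOC and have not switched to other antimicrobials active against NG. Participants who cleared at TOC are not among them.
- Footnote a is the protocol's own wording, not a SAP change, and scoring missing results as failures is the stated convention of these tables.
- The both-positive rule does not recover cumulative clearance. In the first example it shows 50% v 50% where cumulative clearance is 95% v 85%, because it describes only those still positive at TOC.

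All of this stands. A reader might infer that the SAP turns cleared participants into failures, or that the planned comparison points the wrong way. The documents do not support either statement without a condition: both need a reading of one garbled note that overrides the surrounding text and the sampling schedule. What the reply does not remove is that the SAP's note departs from the protocol's with no declared change, and that one analysis population has no condition of its own to prevent the misreading.

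**Conclusion.** The inconsistency is real and lies in text that governs derivation. Its effect is conditional. If the note were programmed as either/or for display 2.338, participants without a Follow-up swab by design would be scored as failures, and the descriptive difference would tilt against the arm with better TOC clearance. In the assumed examples the tilt is 6 to 10 points. The size rests wholly on assumed clearance rates; the direction needs only that later clearance is above zero and equal in the two arms.

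Footnote a is a separate and smaller conflict, limited to participants with no TOC NAAT result and present in both documents.

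The reach is narrow: only the Micro-ITT Pharyngeal Follow-up row is exposed. ME NAAT FU Pharyngeal excludes these participants by definition, Mgen depends on Baseline alone, and the TOC NAAT and culture analyses, including the primary and secondary endpoints, are untouched. The endpoint is exploratory with no formal test, and the SAP itself expects too few Follow-up observations for an adjusted analysis.

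**What to change.** 1. In the note under SAP Table 4, require NG nucleic acid at both Baseline and TOC for pharyngeal NG, and Mgen nucleic acid at Baseline for Mgen.
2. For display 2.338, state that the Micro-ITT Pharyngeal Follow-up denominator is participants NAAT-positive for pharyngeal NG at both Baseline and TOC. Show the others (negative at TOC, or no TOC result) in a separate row, so that they are neither lost nor scored as failures.
3. Align footnote a of SAP Table 3 with the both-positive rule for pharyngeal NG, and note the same clarification for protocol Table 6.

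The cost is SAP wording and one derivation condition, with no new data. It is best done before unblinding. If the analysis has already been programmed, confirm which rule was used and report it.

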7.3.1.6. Additional Microbiology Data

A microbiology database and “Micro Review Aid” (Excel) will be provided for the microbiology reviewer’s guide. All pathogen-level and participant-level microbiological outcome/response data, susceptibility tests results, susceptibility phenotypes, and genotype data (where available) will be combined and displayed together (CLSI and EUCAST).

7.3.2. Analysis Population of Interest

For details of the analysis populations used in each exploratory endpoint, see Section 7.3.1.

7.3.3. Statistical Analyses / Methods

There will be no multiplicity adjustment for the testing of the exploratory endpoints. No formal hypothesis testing will be performed; 95% CIs may be included but only for descriptive purposes. For more details of the analysis methods for each exploratory endpoints, see Section 7.3.1.

7.3.3.1. Subgroup Analyses

Subgroup analyses of certain exploratory endpoints will be performed at the relevant visits for the endpoint, which may include Baseline (BL), TOC, and FU. See Section 5.4.2 for definition of subgroups and Section 7.3.1 for subgroup analysis planned for each endpoint. Subgroup analyses for NAAT outcome and response for NG will only be performed if the corresponding subgroup analysis is conducted in the corresponding primary and secondary endpoint analyses. Additional exploratory analyses may be presented as needed.

All subgroup analyses will follow the same layout/content of the overall population for each endpoint. For subgroup analyses, the summary table will be paginated by each level of the subgroup, and only the unadjusted difference in success rate will be presented.

8. SAFETY ANALYSES

The safety analyses will be based on the Safety population, unless otherwise specified.

8.1. Adverse Events Analyses

All AEs will be collected from the start of treatment until the FU visit and all SAEs will be collected from the signing of the informed consent form until the FU visit based on the timepoints specified in Appendix 1. All reported AEs will be coded using Medical Dictionary for Regulatory Activities (MedDRA) and summarized by system organ class (SOC) and preferred term (PT).

A treatment emergent AE (TEAE) is defined as an AE with start date/time after the first dose date/time of the study treatment. If the time part is missing, only dates will be considered. The number and percentage of TEAEs, study treatment-related AEs, non-serious drug-related AEs, SAEs, and AEs leading to study treatment or study withdrawal will be provided. Any AE starting before the first dose date/time will not be included in any summary analyses but will be displayed in the listings. Therefore, only TEAEs will be included in summary tables with all AEs displayed in listings.

The severity of AEs and SAEs will be determined by the investigator according to the US National Institute of Allergy and Infectious Diseases Division of Microbiology and Infectious Diseases (DMID) criteria for adult toxicity assessment, except for serum creatinine adolescent laboratory data, which will be assessed using DMID pediatric toxicity criteria. Adverse event severity is classified as mild (Grade 1), moderate (Grade 2), severe (Grade 3), potentially life-threatening (Grade 4), or resulting in death (Grade 5). Adverse events starting after the first dose of study treatment with a missing severity will be classified as severe. If a participant reports an AE more than once within the same SOC/PT, the AE with the worst-case severity will be used in the corresponding severity summaries.

The relationship to study treatment, as indicated by the investigator, is classified as “not related” or “related”. Adverse events with a missing relationship to study treatment will be regarded as “related” to study treatment. If a participant reports the same AE more than once within an SOC/PT, the AE with the worst-case relationship to study treatment will be used in the corresponding relationship summaries.

Adverse events analyses including the analysis of AEs, SAEs and other significant AEs will be based on GSK Core Data Standards. All AEs, study drug related AEs, SAEs, and AEs leading to discontinuation of study treatment or withdrawal from study will be provided in separate listings. The listings will capture the hierarchical relationship between SOC, PT, and verbatim term.

In summary tables where AEs are presented by SOC, PT, and maximum grade, SOCs will be sorted in descending order of the total incidence then alphabetically, PTs will be sorted in descending order of the total incidence then alphabetically within the SOC.

In addition, a summary of the number and percentage of participants with common AEs, defined as AEs with $\geq 1\%$ incidence (before rounding) in any treatment group, will be

presented in descending order of total incidence by PT. The incidence of common AEs with relative risk and associated 95% CI (Wald method) will also be summarized in tables and presented graphically by treatment group.

All deaths occurring any time from informed consent through study completions will be listed. Participant-specific details including date of death, cause of death, and whether the death was attributed to a cardiovascular procedure or surgery will be provided.

For completely missing or partial missing AE start date or end date, imputation rules will be applied following Appendix 5. A listing of *Clostridium difficile* laboratory test results will be provided. The details of data displays are presented in Appendix 9.

AE summaries will also be presented for subgroups defined for safety analysis in Section 5.4.2.

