- m. During the Baseline Visit, participants randomly assigned to ceftriaxone plus azithromycin will receive a single IM dose of ceftriaxone (500 mg) plus a single oral dose of azithromycin (1 g). See Section 7.1. Azithromycin should be taken after food consumption and with water.
- n. Record serious adverse events from the time of consent/assent in order to fulfill international regulatory requirements.
- o. Record adverse events from the time of the first dose of study treatment.
- p. Confirm return day/time for the TOC and Follow-up Visits.
- q. Previsit reminder: Study site staff will contact the participant 24 ± 4 hours before the respectively scheduled Baseline (if applicable), TOC, or Follow-up Visit.
- r. Participants who tested positive for CT and/or Mgen per NAAT results at the Baseline Visit should be treated per local standard of care at or after the TOC Visit or at the Follow-up Visit (if treatment has not already been initiated), as required, after all study procedures at the visit have been completed.
- s. Collect sample only if the participant has a signed consent/assent specific for this purpose. The Baseline Visit is the recommended time to collect the sample; however, it can be collected at any time during the study.

Table 2 Collection of Bacteriology and NAAT Microbiological Specimens

Visit	Baseline	TOC ^a	Follow-up	Early Withdrawal
Study Day	1	4 to 8	14 to 21	NA
Collection Type Anatomical Site ^b – Organism	Pre-dose	NA	NA	NA
Bacteriology sample collection ^b				
Urogenital – NG ^c	X	X		X
Pharyngeal – NG ^d	X	X	X ^e	X
Rectal – NG ^d	X	X		X
NAAT assay sample collection ^f				
Urogenital – NG and CT ^g	X	X ^h		X
Urogenital – Mgen ^g	X		X ⁱ	X
Pharyngeal – NG and CT ^j	X	X	X ^k	X
Rectal – NG and CT ^j	X	X		X

CT=*Chlamydia trachomatis*; Mgen=*Mycoplasma genitalium*; NA=not applicable; NAAT=nucleic acid amplification test; NG=*Neisseria gonorrhoeae*; TOC=Test-of-Cure.

- Any participant that withdraws before TOC should have all bacteriology and NAAT assay collections performed as indicated at the TOC Visit.
- Multiple swab specimens and types may need to be obtained from each anatomical site; refer to the laboratory manual.

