12.2.1. Treatment Emergent Flag for Adverse Events

Flag	Definition
Treatment Emergent	
 • If AE onset date/time is on or after treatment start date/time. That is, study treatment start date/time ≤ AE start date/time. If time is missing, only date will be compared.

NOTES:

- All doses of study treatments administered within 24 hours.

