12.5.2.1. Handling of Missing and Partial Dates

Element	Reporting Detail
General	
 Partial dates will be displayed as captured in participant listing displays.
Adverse Events	
 The eCRF allows for the possibility of partial dates (i.e., only month and year) to be recorded for AE start and end dates; that is, the day of the month may be missing. In such a case, the following conventions will be applied for calculating the time to onset and the duration of the event: 
 Missing Start Day: First of the month will be used unless this is before the start date of study treatment; in this case the study treatment start date will be used and hence the event is considered On-treatment as per Appendix 2 Missing Start Time: Midnight 0:00:00 will be used for AEs with missing start time to determine if it's AChE-I.

Element	Reporting Detail
	
 ○ Missing Stop Day: Last day of the month will be used, unless this is after the stop date of study treatment; in this case date the study treatment stop date will be used. ● Completely missing start or end dates will remain missing, with no imputation applied. Consequently, time to onset and duration of such events will be missing. ● Adverse events with entirely missing or unknown start dates will be assumed to be on-treatment and also treatment emergent for reporting purposes.
Concomitant Medications/ Medical History	
 ● Partial dates for any concomitant medications recorded in the CRF will be imputed using the following convention: 
 ○ If the partial date is a start date, a '01' will be used for the day and 'Jan' will be used for the month ○ If the partial date is a stop date, a '28/29/30/31' will be used for the day (dependent on the month and year) and 'Dec' will be used for the month ● The recorded partial date will be displayed in listings.

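### SAP 8.1 counts an AE as treatment-emergent only if it starts after the first dose; SAP Appendix 2 says on or after. The two rules classify Day 1 AEs without a start time differently.

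*SAP*

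**What the plan says.** SAP Section 8.1 states that a treatment-emergent AE "is defined as an AE with start date/time after the first dose date/time of the study treatment", and adds: "If the time part is missing, only dates will be considered". Two further sentences in that paragraph settle what is tabulated: "Any AE starting before the first dose date/time will not be included in any summary analyses but will be displayed in the listings", and "Therefore, only TEAEs will be included in summary tables with all AEs displayed in listings".

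SAP Appendix 2, under the heading Treatment Emergent Flag for Adverse Events, gives a different rule: "If AE onset date/time is on or after treatment start date/time". It spells out the operator: "That is, study treatment start date/time ≤ AE start date/time. If time is missing, only date will be compared".

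The study-phase table in the same appendix uses a strict inequality at treatment start for the On-Treatment phase.

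SAP Appendix 5 deals with AEs whose start day is missing. The first of the month is used unless that precedes treatment start; "in this case the study treatment start date will be used and hence the event is considered On-treatment as per Appendix 2". AEs with no start date at all are taken as treatment-emergent. A missing start time is set to midnight, but only to decide acetylcholinesterase-inhibition (AChE-I) status.

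On collection, the protocol's Schedule of Activities says: "Record adverse events from the time of the first dose of study treatment". SAEs are recorded from consent.

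**The concern.** The difference between *after* and *on or after* looks like a matter of the exact minute of dosing. The date-only rule widens it to the whole of Day 1. An AE dated Day 1 with no time does not start after Day 1, so under the 8.1 definition it is not treatment-emergent and appears only in listings.

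Day 1 is when early effects would be seen. The first gepotidacin dose and both comparator drugs are given then, and Protocol Section 9 notes that the second gepotidacin dose may also fall on Day 1. Protocol Appendix 10 treats diarrhea during dosing or in the 12 hours after it as suggestive of a cholinergic effect. Gastrointestinal and AChE-I events are both AEs of special interest.

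Some outputs turn on small counts. SAP 8.5.2 works with 310 participants exposed to gepotidacin and, when the comparator has no events, shortlists a term at 3 participants. The common-AE table starts at 1%; 310 x 0.01 = 3.1, so 4 participants are needed in an arm of that size. One or two events in or out could change which terms appear.

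**Working it through.** The plan gives no figure to reproduce. The check applies each rule literally.

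**Inputs.** First dose on Day 1 at 10:00 (an arbitrary example). Rule A (SAP 8.1): treatment-emergent if AE start > first dose. Rule B (Appendix 2 flag): treatment-emergent if AE start ≥ first dose. Both compare dates alone when the time is missing. The last column applies 8.1's separate exclusion sentence (AE start < first dose).

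| AE start | Rule A | Rule B | Excluded as before first dose |
|---|---|---|---|
| Day before, no time | no | no | yes |
| Day 1, 09:00 | no | no | yes |
| Day 1, 10:00 (tie) | **no** | **yes** | no |
| Day 1, 14:00 | yes | yes | no |
| Day 1, no time | **no** | **yes** | no |
| Day 2, no time | yes | yes | no |

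The rules disagree in two rows. The exact-minute tie is trivial; the untimed Day 1 AE is not. In both rows 8.1 also disagrees with itself: the AE is not excluded as starting before the dose, yet it does not meet the definition needed to be tabulated.

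**Partial dates.** If the start day is missing and the first of the month precedes treatment start, Appendix 5 sets the AE to the treatment start date. That is again a date tie: no under Rule A, yes under Rule B. An AE with no start date at all counts as treatment-emergent. Literally applied, 8.1 would therefore count an AE with no date and omit one dated Day 1, which cannot be intended.

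**On-Treatment phase.** Appendix 2 defines Pre-Treatment as earlier than treatment start, On-Treatment as strictly later than treatment start up to treatment stop, and Post-Treatment as later than stop. A value equal to treatment start falls in none of the three. Appendix 5 nevertheless relies on this table to call the imputed AEs On-treatment.

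**AChE-I events.** SAP 8.2.3 identifies these by preferred term and a start within 12 hours of the last dose. With midnight imputed, an untimed Day 1 AE meets that window. Whether it is then tabulated depends on whether 8.1's general restriction to treatment-emergent AEs applies on top, which the SAP does not say.

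**Size.** Share of AEs affected = (share starting on Day 1) x (share of those without a start time). The documents give neither term. Purely as an illustration, assume 30% to 80% start on Day 1 and 2% to 30% of those lack a time:

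- low: 0.30 x 0.02 = 0.6%
- middle: 0.50 x 0.10 = 5%
- high: 0.80 x 0.30 = 24%

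A range this wide only shows that the answer depends on an unknown. It also counts events, while most of the tables count participants.

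**The case against.** The case that this is harmless has real weight.

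- The Appendix 2 entry is the flag definition, with an explicit operator and its own missing-time rule, and SAP 5.7 refers data handling to the appendices. A programmer may well follow it and get the right result.
- The exclusion sentence in 8.1 covers only AEs before the first dose, and the next sentence draws its conclusion from that. This suggests that treatment-emergent was meant as everything not before the dose.
- Appendix 5 plainly intends AEs with partial or missing dates to be included.
- AChE-I events have their own algorithm, and SAP 8.5.2 puts all AEs of special interest on the adverse-reaction short list automatically.
- SAP 8.2.3 plans onset summaries in hours, so times are presumably collected.
- Every affected AE remains in the listings.

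All of this stands, and it limits the point. A reader might infer that untimed Day 1 AEs will certainly vanish from every AE summary. The documents do not support that: it follows only if the 8.1 definition is programmed in preference to the Appendix 2 flag, and the SAP does not say which governs. But two current rules that give different tables should not be left to the programmer's choice, and the definition in the main text is the one that gives the wrong answer.

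A reader might also infer that *on or after* can never admit a pre-dose event, because AEs are collected only from the first dose. That holds for non-serious AEs. It is not true of SAEs, which are collected from consent and scheduled at the Day 1 predose assessment.

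**Conclusion.** The 8.1 definition is wrong as written. It conflicts with the Appendix 2 flag for every Day 1 AE without a start time and for partial-date AEs set to the treatment start date. Read literally, it leaves both out of the treatment-emergent summaries while keeping them in the listings. The rest of 8.1 and Appendix 5 indicate that *on or after* was intended.

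The size is unknown. It depends on how often AE start times are missing, which the documents do not state; if nearly all times are recorded, the effect is small. It may be tempting to infer that the rule favours gepotidacin, because early gastrointestinal and AChE-I effects are expected with it. The documents do not support that: the protocol's risk section lists gastrointestinal effects for ceftriaxone and azithromycin as well, and nothing shows that missing times or untimed Day 1 events differ between arms. The primary efficacy analysis is not touched.

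**What to change.** 1. In SAP 8.1, define a treatment-emergent AE as one starting on or after the first dose date/time. State that, when the time is missing, a start date equal to the first dose date counts as treatment-emergent.
2. In the Appendix 2 study-phase table, change the strict < at treatment start in the On-Treatment row to ≤, so that the Appendix 5 cross-reference works and no value falls between phases.
3. State that this single flag is used in all AE, AESI and adverse-reaction summaries, including the AChE-I tables.

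The cost is a few words in the SAP and no new data; it should be settled before unblinding. There is one small downside. Because SAEs are collected from consent, a Day 1 SAE that began before dosing and has no recorded time would be counted as treatment-emergent. Such cases should be rare, and counting them is conservative.
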